2.2 Secondary objectives

The secondary objectives are to assess the clinical course and outcome of adults with COVID-19 who have been treated with Remdesivir with respect to the following:

1. a 7-point ordinal clinical status scale on Day 7 and Day 14
2. timing (from first symptoms and from hospitalisation) and duration of use of Remdesivir
3. clinical severity at Day 7, 14, 28 as assessed by the NEWS 2 score
4. clinical status as assessed a 7-point ordinal scale on Day 28 (or at last observation if discharged or died prior to this time point) in those still hospitalised after Day 14.
5. SpO₂ > 94% on room air on day 7, 14 and 28
6. duration and type (low versus high flow) of oxygen therapy (days)
7. admitted to ICU (yes versus no)
8. number of days spent on ICU/ITU
9. use of mechanical ventilation/ECMO (extracorporeal membrane oxygenation); start and stop dates
10. re-admission with COVID-19 complications or recurrence within 28 days of discharge and outcome (discharged or deceased)

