4.2 Study Variables

All the study variables are summarized in the following table.

	Day1 (Hospital Admission) baseline	Day 7 (+/- 1 day) and Day14 (+/- 2 days) / last observation if discharged or died prior to these time points.	Day 28 or last observation after Day 14 if discharged or died prior to this time point.
Medical History ^a	x		
Pregnancy test	x		
HIV test	x		
Vital Signs ^b	x	x	x
Laboratory Testing ^c	x	x	x
Oxygenation ^d	x	x	x
Clinical Status ^e	x	x	x
Other Treatments for COVID-19 ^f	x	x	x
NEWS SCORE ^g	x	x	x

a. Focused medical history and also the following information (e.g. demographics including ethnicity, baseline characteristics including DM, CV disease and COPD)

b. SpO2, body temperature, body weight and height on admission

c. Includes white blood cell count, creatinine, total bilirubin, ALT, AST at admission Day 7 and day 14 or at discharge if before day 14, radiographic findings at baseline and as available and SARS-CoV-2 PCR, antigen and/or antibody testing.

d. Includes oxygen supplementation: room air, low flow O2 (L/min and %), high flow O2 (L/min and %), non-invasive positive pressure ventilation (FiO2 or %), mechanical ventilation (FiO2 or %), ECMO (extracorporeal membrane oxygenation)

e. The ordinal scale is as: 1. Death, 2. Hospitalised, on invasive mechanical ventilation or ECMO, 3. Hospitalised, on non-invasive ventilation or high flow oxygen devices, 4. Hospitalised, requiring low flow supplemental oxygen, 5. Hospitalised, not requiring supplemental oxygen - requiring ongoing medical care (COVID-19 related or otherwise), 6. Hospitalised, not requiring supplemental oxygen - no longer requires ongoing medical care, 7. Not hospitalised

f. These include corticosteroids, anticoagulants, azithromycin/other antibiotics, anti-inflammatory agents (e.g. Tocilizumab), investigational agents (eg hydroxychloroquine) and immunotherapies such as convalescent plasma and monoclonal antibodies.

g. NEWS 2 score is based on Respiration rate (per minute), SpO2 (%) Air or oxygen. Systolic blood pressure (mmHg), Pulse (per minute) Consciousness, Temperature (°C)

For the purpose of the analyses, partial dates will be extrapolated. For example, all dates saved as NK/FEB/2020 will be recoded as 15/FEB/2020 and those saved NK/NK/2020 will be recoded as 15/JUNE/2020. NK means not known.

5. Sample Size calculation

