Descriptive statistics and graphical representation	
 • Data will be summarized with proportion or median and 95% confidence interval according to the endpoint • Data will be summarized globally and according to disease severity at baseline (ORDSC score 2 vs 3-4 vs 5) • LogRank test will be used to compared the 3 groups • P-values will be two-tailed with a significant level at 5% • Kaplan-Meier curves will be plotted
Statistical analysis	
Kaplan-Meier estimate will be used to estimate the proportion of subject with oxygen therapy and by type (low versus high flow oxygen), the proportion of subjects admitted in ICU and the proportion of those having received mechanical ventilation or ECMO. Time to event will be defined as the time between the date of first symptom and the date of event of interest. Participants not experienced the event of interest will be censored at last observation date. Participants who deceased before will be considered as having the event.
 
The duration (days) of oxygen therapy, the number of days spent in ICU/ITU and the time (days) on mechanical ventilation/ECMO will be estimated using Kaplan-Meier estimates as well as the associated 95% confidence intervals. The time will be defined as the time between the start date of event and the end date of the event of interest or hospital discharge. Subjects who died will be censored at day 28.

Endpoint	8. Duration (days) of hospitalization
----------	----------------------------------------------

Analysis population	
 Full population analysis
Descriptive statistics and graphical representation	
 Data will be summarized with median and 95% confidence interval globally and according to disease severity at baseline (ORDSC score 2 vs 3-4 vs 5) LogRank test will be used to compared the 3 groups P-values will be two-tailed with a significant level at 5% Kaplan-Meier curves will be plotted
Statistical analysis	
Kaplan-Meier method will be used to calculate the medians and the 95% confidence intervals. Time (days) from hospitalization to hospital discharge will be defined as the time between the date of hospitalization for COVID-19 and the date of hospital discharge. The event will be hospital discharge. Subjects who died will be censored at day 28.

9. Other Analyses

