	Alert				
	Verbal				
	Pain				
	Unresponsive				

NEWS 2 score, median (IQR)						
	Low (score 0-4), n(%)					
	Medium (score 5-6)					
	High (score 7 or more)					
COVID Vaccination, n(%)						
Other treatment for COVID-19, n (%)						
	Corticosteroids					
	Tocilizimab/Sarilumab					
	Other COVID Treatment Related Drug					

Table 2. Primary and secondary outcomes

	Overall Total N=xxx	Ordinal Scale Category			
		Score of 2 N=xxx	Score of 3-4 N=xxx	Score of 5 N=xxx	P- value
Mortality over entire study period					
Number of deaths by Day 28					
Kaplan-Meier estimate of mortality by Day 28 – % (95% CI)					
Ordinal Scale at day 7 (± 1 day) – no. (%)					
1					
2					
3					
4					
5					
6					
7					
Ordinal Scale at day 14 (± 2 days) – no. (%)					
1					
2					
3					
4					
5					
6					
7					
Ordinal Scale at day 28 (± 2 days) – no. (%)					
1					
2					
3					
4					
5					
6					
7					
Disease severity assessed by NEWS 2 Score at 7 days					
Total N					
Mean NEWS 2 Score at days 7 (95% CI)					
Disease severity assessed by NEWS 2 Score at 14 days					
Total N					
Mean NEWS 2 Score at days 14 (95% CI)					
Disease severity assessed by NEWS 2 Score at 28 days					

Total N					
Mean NEWS 2 Score at days 28 (95% CI)					
SpO2>94% over first 7 days					
Number of SpO2>94% by Day 7					
Kaplan-Meier estimate of by Day 15 – % (95% CI)					
SpO2>94% over first 14 days					
Number of SpO2>94% by Day 14					
Kaplan-Meier estimate of SpO2>94 by Day 14 – % (95% CI)					
SpO2>94% over entire study period					
Number of SpO2>94% by Day 28					
Kaplan-Meier estimate of SpO2>94 by Day 28 – % (95% CI)					
Median time to SpO2>94% (95% CI) - days					
Oxygen therapy over entire study period (low or high flow)					
Number of oxygen therapy by Day 28					
Kaplan-Meier estimate of oxygen therapy by Day 28 – % (95% CI)					
Median duration on oxygen therapy (95% CI) - days					
Low flow oxygen therapy over entire study period					
Number of low flow oxygen therapy by Day 28					
Kaplan-Meier estimate of low flow oxygen therapy by Day 28 – % (95% CI)					
High flow oxygen therapy over entire study period					
Number of high flow oxygen therapy by Day 28					
Kaplan-Meier estimate of high flow oxygen therapy by Day 28 – % (95% CI)					
ICU admission over entire study period					
Number of ICU admission by Day 28					
Kaplan-Meier estimate of ICU admission by Day 28 – % (95% CI)					
Median duration spent in ICU (95% CI) - days					

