Mechanical ventilation ECMO over entire study period					
Number of Mechanical ventilation ECMO by Day 28					
Kaplan-Meier estimate of Mechanical ventilation ECMO by Day 28 – % (95% CI)					
Median duration on Mechanical ventilation ECMO (95% CI) - days					
Hospitalization					
Hospitalization no					
Median duration on hospitalization (95% CI) - days					
Remdesivir exposure					
Total N					
Median time from first symptom to use of remdesivir (95% CI) - days					
Median time from hospitalization to use of remdesivir (95% CI) - days					
Median duration of use of remdesivir (95% CI) - days					
Readmission					
Number of readmission within 28 days of discharge					

Proportion of re-admission within 28 days of discharge (95% CI)					
Proportion of discharge after readmission (95% CI)					
Proportion of death after readmission (95% CI)

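### Median days on oxygen, in ICU and on ventilation will not measure time on support, because every death is censored at day 28 even when the duration is fully observed

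*SAP*

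**What the plan says.** SAP 8.2 groups the support endpoints together. For the duration endpoints (4.2 oxygen, 6 ICU/ITU, 7.2 ventilation/ECMO) it says that oxygen duration, "the number of days spent in ICU/ITU and the time (days) on mechanical ventilation/ECMO will be estimated using Kaplan-Meier estimates". The time is "the time between the start date of event and the end date of the event of interest or hospital discharge". Death is not listed as an end of the duration. Instead: "Subjects who died will be censored at day 28". No exception is made for a patient whose support stopped at death, or stopped some days before it.

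The three baseline severity groups (ordinal score 2, 3-4 and 5) are compared by log-rank test at the two-sided 5% level. SAP Table 2 shows the results as "Median duration spent in ICU (95% CI) - days" and "Median duration on Mechanical ventilation ECMO (95% CI) - days", with a similar row for oxygen.

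SAP 4.2 sets the visit calendar as "Day1 (Hospital Admission) baseline". SAP 8.2 does not say whether day 28 in the censoring rule is on that calendar or counts from start of support. Protocol 2.2 lists as an objective "use of mechanical ventilation/ECMO (extracorporeal membrane oxygenation); start and stop dates". Nothing elsewhere in the protocol or SAP alters this handling of deaths.

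**The concern.** Censoring is for durations whose end was not seen. Here the end was seen. A patient ventilated for 4 days who dies on the ventilator used 4 days of ventilation. A patient weaned on day 5 who dies on the ward on day 15 also has a complete ventilation time. The rule discards both values and keeps both patients in the risk set as if support continued to day 28.

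The rows would then be read as days of support used, which they are not. The distortion grows with mortality, so it is largest where these figures attract most attention: ventilated patients, ICU patients and those at baseline score 2. A group with more deaths would appear to need support for longer even if its durations were identical.

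**Working it through.** **Inputs.** The SAP gives the start, the end and the handling of deaths (above). The documents give no expected median, no mortality among supported patients and no power statement for these endpoints, so there is no planned figure to reproduce. Mortality among supported patients (q) and the distribution of durations are assumptions, shown over a range.

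**Direction.** Let A(t) be the proportion of supported patients who survive and whose support has ended by time t. Let B(t) be the same for those who die. Before day 28, with day 28 counted from start of support:

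- actual time on support: S_actual(t) = 1 − A(t) − B(t)
- SAP rule: S_rule(t) = 1 − A(t)

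So S_rule(t) ≥ S_actual(t) throughout, and the median can only stay the same or rise. Counting day 28 from admission gives the same direction for deaths up to day 28: each such death turns an event into a censoring at the same or a later time, which cannot lower the curve.

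**Ten-patient example.** Durations are 2, 3, …, 11 days, all observed; the patients with 2, 4, 6 and 9 days die.

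- Actual durations: the curve falls by 0.1 each day from day 2 and reaches 0.5 at day 6. Median 6.
- SAP rule: only the ends at 3, 5, 7, 8, 10 and 11 count, with all four deaths held at risk. The curve is 0.9, 0.8, 0.7, 0.6, 0.5 at days 3, 5, 7, 8, 10. Median 10.

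**Size.** If durations do not depend on death, A(t) = (1 − q)F(t), where F is the distribution function of duration. Setting S_rule = 0.5 gives F(t) = 0.5/(1 − q), so the planned median is that quantile of the durations. Two assumed distributions are shown: gamma with mean 10 and shape 2.5 (median 8.7, or 9 in whole days), and lognormal with median 10 and log-SD 0.7. For the lognormal at q = 0.30: 0.5/0.7 = 0.714, z = 0.566, and 10 × exp(0.7 × 0.566) = 14.9.

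| q | 0.5/(1 − q) | Gamma quantile | Gamma, whole days | Lognormal quantile |
|---|---|---|---|---|
| 0 | 0.500 | 8.7 | 9 | 10.0 |
| 0.05 | 0.526 | 9.1 | about 9 | 10.5 |
| 0.10 | 0.556 | 9.5 | 10 | 11.0 |
| 0.20 | 0.625 | 10.7 | 11 | 12.5 |
| 0.30 | 0.714 | 12.4 | 13 | 14.9 |
| 0.40 | 0.833 | 15.6 | 16 | 19.7 |
| 0.50 | 1.000 | not reached | about 27 to not reached, by clock | not reached |

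**Which day 28.** In simulations of 20,000 patients, medians with day 28 counted from admission and from start of support agreed, or differed by at most a day, up to 40% mortality. With gamma durations on the admission clock at 30% mortality, the median was 12 to 13 days for support starting anywhere from Day 1 to Day 15, and fell to 10 to 11 only for starts on Day 20. At 40% it was 16 for starts on Days 1 to 10 and 14 for Day 15.

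**Group comparison.** Take two groups with identical durations but mortality of 20% and 40%. Under the rule, the rate of coming off support starts in the ratio (1 − 0.40)/(1 − 0.20) = 0.75, although time on support does not differ. In simulation the log-rank test gave p < 0.05 in 46% of runs with 50 per group and 75% with 100 per group. A repeat with the gamma durations above gave 52% and 82%. Analysing actual durations gave about 5%.

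**The case against.** The strongest defence is that this is a choice of estimand. Holding deaths in the risk set to a fixed horizon is a recognised way to estimate time to coming off support alive, and it stops early death from looking like quick recovery. The SAP takes a similar line elsewhere: deaths are held to day 28 for SpO2 recovery and for hospital stay, and are given a NEWS 2 score of 20. For hospital stay the rule is coherent, because discharge is named as the event and the clock starts at admission, although that table row is also labelled as a duration. The defence shows that the method has a legitimate use. It does not rescue these rows, which the SAP defines and labels as time on support, not as time to liberation alive.

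It is also fair that counting death as the end of support has the opposite weakness: early deaths shorten the overall figure in the sickest patients. That stands, and is why the fix includes a split by vital status.

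A reader might infer that the mismatch between the admission calendar and the support clock causes the inflation, or that groups starting support earlier will look far worse. The documents do not establish which clock applies, and the calculation shows that the choice barely moves medians up to about 40% mortality unless support starts very late. Holding deaths to the horizon is what drives the effect.

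**Conclusion.** The point stands. The planned medians for oxygen, ICU/ITU and ventilation/ECMO do not estimate days on support. They equal or exceed the actual median, and the severity comparison mixes mortality with duration. The direction follows from the rule for deaths up to day 28; the size rests on assumed mortality and an assumed duration distribution that is the same for survivors and deaths.

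It would be too strong to say that all three medians will be materially inflated. At 5-10% mortality the shift is about a day or less, so overall oxygen duration may hardly change. From about 30% mortality it becomes large: 9 to 13 days in the gamma case, 10 to 15 in the lognormal.

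The unstated origin of day 28 is a gap in specification with little effect on most medians. These are secondary endpoints in a study with no formal hypothesis, and 28-day mortality is unaffected. The correction should be made, but it does not threaten the main result.

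**What to change.** 1. For endpoints 4.2, 6 and 7.2, define duration as start of support to stop, hospital discharge or death, whichever is first. Report median and quartiles overall and separately for survivors and non-survivors. Censor only patients whose support is still running at last observation.
2. If time to coming off support alive is wanted, add it as a separate row under that name: cumulative incidence with death as a competing event, with the time origin and horizon stated. Compare severity groups with a method suited to that quantity.
3. State whether day 28 counts from admission or from start of support wherever it is used as a horizon for these endpoints.
4. Relabel the Table 2 rows to match.

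The cost is SAP wording and a few table rows. The dates needed are those the SAP definition already uses, plus date of death, which the primary analysis requires. Start and stop dates are explicit in the protocol for ventilation/ECMO; for oxygen and ICU they are implied by the SAP definition, so their presence in the eCRF should be confirmed.

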2. OBJECTIVES AND OUTCOME MEASURES/ENDPOINTS

2.1 Primary objective

The primary objectives of this study are to assess the clinical course and outcome of adults with COVID-19 who have been treated with Remdesivir assessed by:

1. all-cause mortality at Day 28
2. duration of hospitalisation

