Secondary 
 a 7-point ordinal clinical status scale on Day 7, 14 and 28 (or at last observation if discharged or died prior to this time point) clinical severity at Day 7, 14, 28 as assessed by the NEWS 2 score $\text{SpO}_2 > 94\%$ on room air on day 7, 14 and 28 duration and type (low versus high flow) of oxygen therapy (days) admitted to ICU (yes versus no) number of days spent on ICU/ITU use of mechanical ventilation/ECMO (extracorporeal membrane oxygenation); start and stop dates duration of hospitalisation timing (from first symptoms and from hospitalisation) and duration of use of Remdesivir re-admission with COVID-19 complications or recurrence within 28 days of discharge and outcome (discharged or deceased) 	
 Disease state on a 7-point scale defined as 1. death, 2. hospitalised, on invasive mechanical ventilation or ECMO, 3. hospitalised, on non-invasive ventilation or high flow oxygen devices, 4. Hospitalised, requiring low flow supplemental oxygen, 5. hospitalised, not requiring supplemental oxygen - requiring ongoing medical care (COVID-19 related or otherwise), 6. hospitalised, not requiring supplemental oxygen - no longer requires ongoing medical care, 7. not hospitalised at Day 7 and 14, and 28 (or at last observation if discharged or died prior to this time point) Occurrence of disease severity at day 7, 14, 28 as assessed by NEWS2 score SpO_2 on room air on day 7, 14, and 28 
 Occurrence of $\text{SpO}_2 > 94\%$ on room air on day 7, 14 and 28 Time to $\text{SpO}_2 > 94\%$ on room air Oxygen therapy over the 28 days 
 Frequency of oxygen therapy overall and by type (low versus high flow oxygen) Duration (days) of oxygen therapy Frequency of ICU admission Number of days spent in ICU/ITU Mechanical ventilation over the 28 days

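### Duration of hospitalisation gives the dead a Day 28 horizon but the living none, so if discharges after Day 28 are used, the median stay can be too short in any group with fewer than half home by then

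*SAP*

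**What the plan says.** SAP 8.2, endpoint 8, measures "the time between the date of hospitalization for COVID-19 and the date of hospital discharge". The estimator is stated as "Kaplan-Meier method will be used to calculate the medians and the 95% confidence intervals", reported as "median and 95% confidence interval globally and according to disease severity at baseline" (ordinal score 2, 3-4 or 5), and "LogRank test will be used to compared the 3 groups". The event and the handling of deaths are set in two sentences: "The event will be hospital discharge. Subjects who died will be censored at day 28". There is no upper limit on the time to discharge and no censoring rule for a patient who is alive and still in hospital.

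The row in SAP Appendix Table 2 is "Median duration on hospitalization (95% CI) - days", with no Day 28 limit. By contrast, the endpoint list in SAP 3 restricts some other items, for example "Oxygen therapy over the 28 days".

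The rank of the endpoint differs between places. Protocol 2.1 names "duration of hospitalisation" as a primary objective, Protocol 2.4 lists it as the ninth secondary criterion, and the SAP treats it as a secondary endpoint.

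**The concern.** Holding deaths in the risk set to a fixed day is a recognised way to treat them as never discharged. It works only if follow-up of everyone else stops on the same day. Read literally, endpoint 8 stops the clock at Day 28 for the dead only. All deaths leave the risk set together at that point, including deaths after Day 28, which are pulled back to it. Those still at risk are patients who will eventually survive. From then on Kaplan-Meier treats the dead as if they would have been discharged at the survivors' rate.

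At stake is the median stay in the sickest group, where a long or unreached median is the informative result. The log-rank test would also add contributions from survivor-only risk sets after Day 28 to contributions from all patients before it.

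**Working it through.** The documents state no expected median, mortality or discharge rate, so there is no figure of the plan's to reproduce. The rule comes from SAP 8.2; every rate below is an assumption.

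**Step 1: up to Day 28.** Let d be the share of a group discharged by Day 28. The dead stay in the risk set, so with no earlier censoring S(28) = 1 - d. This equals 1 minus the cumulative incidence of discharge, which is correct.

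**Step 2: after Day 28 under the SAP rule.** S(t) = (1 - d) × (share of the remaining survivors not yet discharged). The curve reaches 0.5 once a share 1 - 0.5/(1 - d) of those survivors has gone home. The number of deaths does not enter. The required share is:
- d = 0.20: 1 - 0.5/0.80 = 37.5%
- d = 0.30: 1 - 0.5/0.70 = 28.6%
- d = 0.40: 1 - 0.5/0.60 = 16.7%
- d = 0.45: 1 - 0.5/0.55 = 9.1%

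**Step 3: size.** Assume a further share l is discharged evenly over Days 29-60 (32 days), the rest die, and all survivors are followed to discharge. Then:
- SAP median = 28 + 32 × [1 - 0.5/(1 - d)]
- Day when half of all patients are home = 28 + 32 × (0.5 - d)/l, which exists only if d + l is at least 0.5

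| d | l | Dead | SAP median | Half of all patients home |
|---|---|---|---|---|
| 0.25 | 0.30 | 0.45 | 28 + 32 × 0.333 = 38.7, Day 39 | 28 + 32 × 0.25/0.30 = 54.7, Day 55 |
| 0.25 | 0.20 | 0.55 | 38.7, Day 39 | never (45% ever home) |
| 0.35 | 0.30 | 0.35 | 28 + 32 × 0.231 = 35.4, Day 36 | 28 + 32 × 0.15/0.30 = 44.0, Day 44 |
| 0.40 | 0.35 | 0.25 | 28 + 32 × 0.167 = 33.3, Day 34 | 28 + 32 × 0.10/0.35 = 37.1, Day 38 |

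Simulating 100,000 stays per scenario gives 39 vs 55, 39 vs not reached, 36 vs 45 and 34 vs 37. These agree with the table to within a day.

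**Step 4: product-limit curves on assumed groups of 100**, with late discharges spread over Days 30-60.
- 30 home by Day 28, 15 later, 55 dead: the SAP rule gives 39 days and the curve ends at 0. With a common Day 28 cap the median is not reached (S(28) = 0.70). By cumulative incidence it is also not reached (the curve ends at 0.55).
- 40 home by Day 28, one later, 59 dead: only one patient is at risk after Day 28, so that one discharge takes the curve from 0.60 to 0 and the SAP median is 30 days.
- 40 home by Day 28, 15 later, 45 dead: 34 days under the SAP rule, 49 by cumulative incidence.

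**Step 5: where it does not happen.**
- 45 home by Day 28, none later, 55 dead: S stays at 0.55, not reached under the SAP rule.
- 30 home by Day 28, three later, 55 dead, 12 still in hospital at data cut: 0.70 × 12/15 = 0.56, not reached.
- 80 home by Day 28, eight later, 12 dead: 19 days under the SAP rule, the cap and cumulative incidence alike.

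**The case against.** The strongest reply is that a Day 28 horizon is implied. Day 28 is the last column of the data schedule (Protocol 5, SAP 4.2). Table 2 pairs the entire study period with Day 28 counts for mortality, oxygen, ICU and ventilation. SAP 7.1 counts discharges and deaths before Day 28. Censoring deaths at Day 28 is itself the usual device for a 28-day window. On that reading living inpatients are censored at Day 28 too, and the median is correctly not reached.

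This reading is possible, but no passage applies it to endpoint 8, and some text points the other way. For the primary endpoint, SAP 8.1 censors patients alive at Day 28 at their last observation, not at Day 28. Readmission is followed for 28 days after discharge, which for a Day 28 discharge means Day 56. Admissions began after 31 August 2020 and the final analysis is set for July-September 2021, so many late discharge dates could be on record. None of this proves that they are collected: readmission follow-up concerns patients already discharged. The contrast with oxygen and ventilation is also weak evidence of a deliberate choice, because their 28-day label stands only in the endpoint list, ICU days lack it too, and the analysis text for those durations carries the same sentence on deaths with no explicit cap.

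Two stronger readings should be resisted. A reader might infer that this is the familiar error of censoring at the date of death. It is not: up to Day 28 the rule is right. A reader might also infer that the plan always prints a finite median where fewer than half go home. Step 5 gives two counterexamples. The finite median needs recorded discharges after Day 28 in enough of the remaining survivors.

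**Conclusion.** The point holds as a conditional one. As written, endpoint 8 ends follow-up at Day 28 for the dead and leaves it open for the living. If discharges after Day 28 enter the analysis, the median can be too short, or finite when none exists, in any group with fewer than half discharged by Day 28. Under the assumed rates the shortfall runs from about 3 to 16 days, plus the case with no true median. All of these sizes rest on assumed death and discharge rates and on late discharges spread evenly to Day 60.

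The reach is limited. Groups with a median below 28 days keep a correct median, so probably one severity row is affected. The log-rank effect is real in kind but not quantified here, and SAP 2 states no formal hypothesis. The documents do not support calling this a fault in the study's main result: stay is a primary objective only in Protocol 2.1, and the SAP's primary endpoint is 28-day mortality. It should still be settled before analysis, because two analysts following the present text could print different medians for the sickest group.

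**What to change.** In SAP 8.2, endpoint 8, apply one horizon to everyone. All patients not discharged alive by Day 28, whether dead or still in hospital, are censored at Day 28, and a median not reached is reported as >28 days. Label the Table 2 row to match.

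If stays beyond Day 28 are wanted, report instead the Aalen-Johansen cumulative incidence of discharge alive with death as the competing event, compare groups with Gray's test, and state when living inpatients are censored.

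The cost is about two sentences in the SAP. The downside is that the score 2 group may have no numerical median.
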